5.2 Definition of compliance with the self-administered oral agent ESK981

Based on pill counts made by the Research Coordinator from the bottles of ESK981 returned by the patient, the % of intended ESK981 pills presumably consumed will be calculated. If that % is $\geq 75\%$ over Cycle 1 (the first 28 days of ESK981 treatment), then the patient will be deemed "compliant" with the intended oral ESK981 treatment regimen.

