6.5 Dose Modifications

Patients with NCI-CTCAE Grade 3 or Grade 4 adverse events judged to be (at least possibly) related to ESK981 will have their ESK981 held until the adverse event resolves to Grade 2 or lower. Standard management of adverse events should be utilized. Patients may then be restarted on ESK981 at a reduced dose of 120mg (3 capsules) daily for 5 days, 2 days off. Following a dose reduction, patients who have a second NCI-CTCAE Grade 3 or Grade 4 adverse event judged to be at least possibly related to ESK981 will be discontinued from the study. If drug cannot be restarted within 3 weeks of being held, ESK981 should be discontinued. Patients will also be discontinued for any of the following reasons:

1. Worsening symptoms that can be attributed to prostate cancer
2. Unacceptable adverse event(s) including development of a urinary outlet obstruction requiring urinary catheterization and/or surgical intervention,
3. Intercurrent illness that prevents further participation,
4. Patient refuses further treatment through the study and/or withdraws consent to participate,
5. Patient is noncompliant with respect to taking drugs, keeping appointments, or having tests required for the evaluation of drug safety and efficacy, or
6. General or specific changes in the patient's condition that render the patient unacceptable for further treatment in this study in the judgment of the investigator.

Under no circumstance will care of a withdrawn patient be adversely affected by a decision to withdraw or be withdrawn from the study

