11.3 Design

11.3.1 We will utilize a single group single-stage Phase II design for the study. Patients will receive 160mg (4 capsules) of ESK981 dosed once daily for five consecutive days followed by a two consecutive day treatment break, for a cycle of 28 days. After 8 weeks (2 cycles) of ESK981, patients will be evaluated for their rate of PSA decline of $\geq 50\%$ from baseline (PSA50), using the PCWG3 criteria. Extrapolating from the data summarized on PSA50 response at any time by Cheng et al,¹⁶ we hypothesize that the 8-week PSA50 rate in patients similar to patients eligible for this protocol is approximately 20%. We also hypothesize that the 8-week PSA50 rate for ESK981 treated patients will be approximately 30%.

11.3.2 We seek preliminary evidence that the true 8-week PSA50 rate for patients on ESK981 exceeds the hypothesized reference value of 20%. Having a directional hypothesis, the PSA50 rate will be estimated with a 1-sided Wilson type 90% lower confidence interval (CI). With precision defined as a CI half-width (distance from the PSA50 estimate to the lower 90% confidence limit (CL)) of 0.100, a sample size of N=27 patients and a sample estimate of PSA50 = 30% would have a lower CL = 0.201. This would indicate that the true 8-week PSA50 rate was $> 20\%$, with 90% confidence.

11.3.3 The required sample size of N=27 was determined from the "Confidence Intervals for One Proportion" program within the PASS 15 software.¹⁷

11.3.4 Sample size adjustment for non-compliance will be made as follows. A major goal of this study is to evaluate the efficacy (in addition to the effectiveness) of ESK981 upon the PSA50 rate, safety, and tolerability. For each individual patient, we will allow for an ESK981 treatment non-compliance of up to 25% (i.e., up to 25% of pills were not taken).

Our initial analytic focus will be on the patients who are eligible (per Section 3), and evaluable (i.e., were on treatment for at least Cycle 1 [28 days]), and compliant (took at least 75% of the intended ESK981 pills during Cycle 1).

The patients meeting all 3 such requirements will be considered the eligible, evaluable, and compliant ("EEC") subset. We anticipate that up to 15% of the enrolled patients will not become EEC for one reason or another.

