To obtain the requisite 27 ESK981 compliant patients (i.e., completely EEC) allowing for an overall attrition rate ("a") of up to 15% of patients, we will need to enroll up to $N' = [N / (1 - a)] = [27 / (1 - 0.15)] = 27 / 0.85 = 32$ patients.

The consequence of non-compliance (i.e. not being completely EEC) is that such patients would still be utilized in analyses of the effectiveness of ESK981. For example, that would focus on the patients who were "EE" but not compliant. Another effectiveness analysis would focus on the patients who were eligible, but neither evaluable or compliant. All of these analyses of non-EEC patients would be viewed as *sensitivity analyses* of the efficacy analysis of only the EEC patients. These supplemental analyses would provide a more complete assessment of the feasibility and efficacy *combined* of the oral ESK981 treatment in this study population.

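### Section 11.3.4 can be read as taking the lead safety and tolerability rates from the eligible, evaluable and compliant (EEC) subset, and no all-treated safety population is defined

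*Combined protocol and SAP*

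**What the plan says.** Safety and tolerability is the second primary objective (Sections 2.1 and 11.1), and toxicities are the second primary endpoint (Section 11.2.1).

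- **Goal (11.3.4).** The section describes a major goal as evaluating efficacy, as well as effectiveness, "upon the PSA50 rate, safety, and tolerability".
- **Lead set (11.3.4).** The same section continues: "Our initial analytic focus will be on the patients who are eligible (per Section 3), and evaluable", and compliant. Evaluable means on treatment for at least the 28 days of Cycle 1. Compliant means the man "took at least 75% of the intended ESK981 pills during Cycle 1". No endpoint is exempted.
- **Men outside EEC (11.3.4).** They are used in analyses of effectiveness, with two subsets given as examples. "All of these analyses of non-EEC patients would be viewed as" sensitivity analyses of the EEC efficacy analysis.
- **Safety analysis (11.4.1).** Adverse events are tabulated by incidence and severity, with two-sided confidence intervals for toxicity. Neither the population nor the confidence level is given.
- **Compliance (5.2).** From returned bottles, "the % of intended ESK981 pills presumably consumed will be calculated". Nothing says what happens to the intended count when the protocol itself stops or lowers dosing.
- **Holds (6.5).** Men with a related Grade 3 or 4 event "will have their ESK981 held until the adverse event resolves to Grade 2 or lower". They may restart at 3 capsules daily. They are discontinued if drug cannot be restarted within 3 weeks, or after a second such event following the reduction.

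No safety or all-treated population is defined. Intent-to-treat appears only as a glossary entry in Appendix D.

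**The concern.** For an efficacy endpoint, a compliant subset answers a narrower question but a coherent one. For a toxicity endpoint, membership of the subset depends on the outcome being measured, because toxicity is one of the reasons men stop or miss drug in Cycle 1. A rate computed only in men who stayed on drug and took most of it omits some of the events that the second primary objective is meant to count.

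The only population text that mentions safety points to EEC, and the section that plans the safety analysis does not correct it. An analyst following the document could produce an EEC toxicity table as the lead result and be within the plan.

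**Working it through.** **1. The plan's own figures.**
- Enrolment: 27 / (1 − 0.15) = 27 / 0.85 = 31.76, rounded up to 32, as in 11.3.4.
- Wilson one-sided 90% lower limit at p = 0.30, n = 27, z = 1.2816: 0.2011, which matches the stated 0.201.

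Both reproduce and neither is in dispute. They imply up to 32 − 27 = 5 men outside EEC.

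**2. Route out of EEC by stopping.** Evaluable requires 28 days on treatment. A man who discontinues for toxicity before Day 28 fails this whatever his pill count.

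**3. Route out of EEC by a hold.** Planned dosing is "160mg (4 capsules) of ESK981 dosed once daily for five consecutive days", then two days off. Over Cycle 1 that is 5 × 4 = 20 dosing days and 20 × 4 = 80 capsules. The 75% threshold is 0.75 × 80 = 60. Assume a 7-day hold, restart at 3 capsules daily, and an intended count that stays at 80:

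| Hold starts | Capsules taken | Share of 80 | Compliant? |
|---|---|---|---|
| Day 1 | 0 + 15 + 15 + 15 = 45 | 56.3% | No |
| Day 8 | 20 + 0 + 15 + 15 = 50 | 62.5% | No |
| Day 15 | 20 + 20 + 0 + 15 = 55 | 68.8% | No |
| Day 19 | 14 days × 4 + 1 day × 3 = 59 | 73.8% | No |
| Day 20 | 15 days × 4 + 0 = 60 | 75.0% | Yes |
| Day 22 | 15 days × 4 + 0 = 60 | 75.0% | Yes |

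Every start from Day 1 to Day 19 gives 45 to 59 capsules and fails. Starts from Day 20 reach at least 60 and pass. If the intended count is reset to what was prescribed after the hold, the same men could score 100% and this route closes. Section 5.2 does not say which count applies.

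**4. Effect on the rate.** These counts are assumed, not taken from the plan: 32 men treated, 27 in EEC, and 5 EEC men with a Grade 3 or 4 event. The EEC rate is 5/27 = 18.5%. The two-sided 90% Wilson interval is

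(p + z²/2n ± z√[p(1 − p)/n + z²/4n²]) / (1 + z²/n), with z = 1.645,

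which gives 9.3% to 33.5%. The 90% level is also an assumption.

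| Excluded men with an event | All-treated rate |
|---|---|
| 0 of 5 | 5/32 = 15.6% |
| 1 of 5 | 6/32 = 18.8% |
| 2 of 5 | 7/32 = 21.9% |
| 3 of 5 | 8/32 = 25.0% |
| 4 of 5 | 9/32 = 28.1% |
| 5 of 5 | 10/32 = 31.3% (90% Wilson 19.7% to 45.7%) |

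The two rates are almost equal when one excluded man has an event. With none, the EEC rate is the higher. With two or more, it is the lower.

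**The case against.** The best defence is that EEC was meant for efficacy only. The phrase naming safety is a goal statement in a paragraph about inflating the sample size. Section 11.3.4 later calls the EEC analysis an efficacy analysis, and Section 11.4.1 places no EEC restriction on adverse events. An initial focus is also not an exclusive one. This stands in part. A reader might infer that the plan commits the toxicity rates to EEC men only. The documents do not go that far: an all-treated table is neither prohibited nor provided for. What remains is that safety is named in the same paragraph as the EEC focus, with no other population offered for a primary endpoint.

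Three further inferences are tempting and should be resisted.

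- *That the rate is certainly too low.* Section 11.3.4 expects men to miss EEC for various reasons. If none of the excluded men had an event, the illustration gives 15.6% among all treated, below the EEC figure.
- *That EEC means men who tolerated Cycle 1.* Men with a hold starting late in Cycle 1, or with toxicity after Cycle 1, stay in. The hold route also depends on how intended pills are counted. The pill diary in Appendix E records the prescribed daily dose and pill number for each cycle, which is compatible with a count that follows the prescription.
- *That men outside EEC are never pooled with the rest.* The subsets in 11.3.4 are introduced as examples, so pooling is left open.

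It is also fair to say that the data will exist. Section 7.2.1 has all observed adverse events recorded, Section 7 pauses enrolment to review the first six men, and Appendix F reports Grade 3 to 5 events. Those provisions govern collection and monitoring. They do not set the denominator of the final analysis.

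**Conclusion.** The point holds as a defect in the stated analysis population for a primary endpoint. Sections 11.3.4 and 11.4.1 together allow the lead toxicity rates to be taken from a subset whose membership can depend on toxicity.

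- Exclusion of men who stop for toxicity before Day 28 follows from the definition of evaluable and needs no further assumption.
- Exclusion through a protocol hold is conditional on intended pills meaning the original 80 capsules. For a 7-day hold followed by the reduced dose, it is also conditional on a start by Day 19.
- The downward bias is conditional on toxicity driving the exclusions. In the illustration, 18.5% in EEC sits against 15.6% to 31.3% among all treated. The upper end requires all five excluded men to have had an event. The event counts are assumed; the five excluded men are the plan's own 15% allowance.

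The sample size and the PSA50 precision calculation are unaffected.

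**What to change.** 1. In Section 11.3.4, limit the EEC focus to PSA50 by taking safety and tolerability out of the goal sentence that leads into it.
2. In Section 11.4.1, state that all adverse event tabulations and toxicity confidence intervals use every patient who received at least one dose of ESK981. An EEC table may follow as supportive only.
3. In Section 5.2, state how intended pills are counted when drug is held or reduced under Section 6.5, so that compliance is determined the same way for every man.

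The cost is a few sentences of wording and possibly less favourable reported toxicity rates. No patients are added, no further data are collected, and the sample size does not change.

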8.3.5 Evaluating best overall response

The best overall response is the best response recorded from the start of treatment until either disease progression or recurrence. The investigator's determination of best overall response will be based both on response criteria and on confirmation criteria (Table 9). To be assigned a status of partial response or complete response, changes in tumor measurements must be confirmed by repeat assessment performed 4-6 weeks after the criteria for response are first met. To confirm stable disease, follow-up measurements must meet SD criteria at a minimum interval of 6-8 weeks after SD was first documented.

Note: If unconfirmed progression noted at the first time point is not confirmed at a second time point, the next assessment time point after the first that meets the criteria for progression will be treated as time point 1.

Table 9. Assessing Overall Response.

Target Lesions	Nontarget Lesions	New Lesions	Overall Response
CR	CR	No	CR
CR	Incomplete response/SD	No	PR
PR	Non-PD	No	PR
SD	Non-PD	No	SD
PD	Any	Yes or No	PD
Any	PD	Yes or No	PD
Any	Any	Yes	PD

Abbreviations: CR, complete response; PD, progressive disease; PR, partial response; SD, stable disease.

Subjects with global deterioration of health status who require treatment to be discontinued without objective evidence of disease progression should be classified as having symptomatic deterioration. Every effort should be made to document their objective progression, even after discontinuing treatment.

Subjects who do not have tumor response assessment due to rapid progression or toxicity will be considered nonresponders, will be included in the denominator for the response rate, and will be classified into one of the categories listed below:

- death attributed to disease progression
- early discontinuation attributed to disease progression
- death attributed to drug toxicity
- early discontinuation attributed to drug toxicity

Note: If a subject receives subsequent therapy before tumor progression is documented, the reason for changing therapy must be reported. Reasons include clinical progression, drug toxicity, or secondary therapy for maintaining tumor response.

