11. STATISTICAL CONSIDERATIONS

11.1 Objectives

The **primary objectives** of this study are:

- 1) To determine the PSA $\geq 50\%$ response rate (PSA50) from baseline using the PCWG3 criteria to ESK981 as a single agent in men with mCRPC who have progressed on enzalutamide (an oral androgen-receptor inhibitor) and/or abiraterone acetate (an androgen synthesis inhibitor).
- 2) To assess the safety and tolerability of ESK981 as a single agent.

The **secondary objectives** of this study are:

- 1) To determine the time to PSA response (TTPR) to ESK981 in patients with mCRPC
- 2) To determine the duration of PSA response (PRD) to ESK981 in patients with mCRPC
- 3) To determine PSA progression rates as defined by the PCWG3 criteria.
- 4) To determine PSA progression free survival (PPFS) as defined by the PCWG3 criteria.

The **correlative/exploratory/tertiary objectives** of this study are: to assess exploratory biomarkers from blood and tumor biopsies. Examples of these may include, but are not limited to: whole exome sequencing, capture whole transcriptome analysis, AR and ARv7 analysis, ki-67, apoptosis, etc.

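### Section 11.3.4 leads the PSA50 analysis with a subset selected after treatment starts, and no PSA50 rate over all eligible treated patients is defined

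*Combined protocol and SAP*

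**What the plan says.** **Lead set.** Section 11.3.4 directs the first analysis to patients who are eligible, "evaluable (i.e., were on treatment for at least Cycle 1 [28 days]), and compliant (took at least 75% of the intended ESK981 pills" in Cycle 1). These are the eligible, evaluable and compliant (EEC) patients.

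**Sample size.** The planned N counts members of that subset. Enrolment of up to 32 is set as follows: "To obtain the requisite 27 ESK981 compliant patients (i.e., completely EEC"). The allowance is stated as: "We anticipate that up to 15% of the enrolled patients will not become EEC for one reason or another".

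**Patients outside EEC.** They are kept for supplementary work, described as sensitivity analyses of "the efficacy analysis of only the EEC patients". Two are offered as examples. One takes eligible, evaluable patients who were not compliant. The other is described thus: "Another effectiveness analysis would focus on the patients who were eligible, but neither evaluable or compliant".

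**Analysis section.** Section 11.4.1 gives the estimator and the one-sided 90% Wilson limit but names no analysis set.

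**Question asked.** The objective in 11.1 concerns PSA50 "in men with mCRPC who have progressed on enzalutamide" and/or abiraterone. Sections 11.3.1 and 11.3.2 speak of the rate in patients treated with ESK981. The reference is worded as the "8-week PSA50 rate in patients similar to patients eligible for this protocol is approximately 20" per cent.

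**Tumour response.** Section 8.3.5 says that subjects with no tumour assessment "due to rapid progression or toxicity will be considered nonresponders, will be included in the denominator for the response rate".

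**The concern.** Being on drug for 28 days and taking three quarters of the Cycle 1 pills are both observed after treatment starts. A man who stops in Cycle 1 because of toxicity, progression, withdrawal or death is removed from the lead denominator instead of counting as a non-response. Neither the objective nor the target rate for ESK981-treated patients carries a 28-day or adherence condition, so the lead estimate answers a narrower question than the one posed.

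The trial has no control arm: one observed rate is read against a fixed 20%. If men who leave early respond less often than those who stay, the rate set against 20% is too high as a description of eligible treated men. The two named sensitivity analyses do not repair this, because each describes an excluded group by itself. At full attrition the excluded groups hold about five men in all (32 − 27).

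**Working it through.** **1. The plan's own figures.** Inputs from 11.3.2 and 11.3.4: N = 27, estimate 30%, one-sided 90% Wilson limit (z = 1.2816), attrition 15%.

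L = [p + z²/2n − z√(p(1−p)/n + z²/4n²)] / (1 + z²/n)

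At p = 0.30 and n = 27, L = 0.2011, half-width 0.0989. The plan gives 0.201 and a target half-width of 0.100. At n = 26 the half-width is 0.1004, so 27 is the smallest N that meets the target. Enrolment: 27/0.85 = 31.76, rounded up to 32. Both figures reproduce.

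**2. Responders needed for a lower limit above 0.20.**

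| N | largest count that fails | smallest count that passes |
|---|---|---|
| 27 | 8 (0.198) | 9 (0.230) |
| 30 | 8 (0.177) | 9 (0.205) |
| 31 | 9 (0.199) | 10 (0.226) |
| 32 | 9 (0.192) | 10 (0.219) |

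The threshold is 9 for N = 27 to 30 and 10 for N = 31 to 32.

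**3. Bias in the EEC rate.** Let e be the share of eligible treated patients excluded after baseline, and r the response rate of excluded patients divided by that of EEC patients. The documents give no value for r, so it is varied. With a true rate of 20% in eligible treated patients,

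q(EEC) = 0.20 / [(1 − e) + e·r]

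| e | r = 0 | r = 0.5 | r = 1 |
|---|---|---|---|
| 5% | 21.1% (+1.1 points) | 20.5% (+0.5) | 20% |
| 10% | 22.2% (+2.2) | 21.1% (+1.1) | 20% |
| 15% | 23.5% (+3.5) | 21.6% (+1.6) | 20% |

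**4. Chance of a lower limit above 0.20 when the true rate is 20%.** Take 27 EEC patients plus 2 to 5 eligible treated exclusions. The EEC columns are P(X ≥ 9 | 27, q), with e = 2/29, 3/30, 4/31 and 5/32. The last column is P(X ≥ threshold | N, 0.20).

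| Eligible treated N | EEC, r = 0 | EEC, r = 0.5 | Eligible-treated set |
|---|---|---|---|
| 29 | 10.6% | 8.8% | 10.8% |
| 30 | 12.5% | 9.6% | 12.9% |
| 31 | 14.7% | 10.4% | 7.5% |
| 32 | 17.0% | 11.2% | 9.0% |

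The last column moves unevenly because the threshold steps from 9 to 10 between N = 30 and N = 31. The bottom row has e = 15.6%, slightly above the plan's 15%, because enrolment was rounded up.

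**5. One given data set, all exclusions non-responders.** 9/27 gives 0.230 and 9/30 gives 0.205, both above 0.20. 9/31 gives 0.199 and 9/32 gives 0.192, both below. With 8 responders neither set passes; with 10 both pass. The conclusion therefore changes only at exactly 9 responders with at least 4 eligible treated exclusions.

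**The case against.** EEC is a declared choice. Section 11.3.4 says that efficacy is to be studied in addition to effectiveness, fixes the thresholds in advance and labels the other analyses as sensitivity analyses. That is a recognisable evaluable-patient estimand for a Phase II trial seeking preliminary evidence. Early leavers are not hidden either: PSA is drawn on days 8, 15 and 22, and section 8.2.1 recommends reporting each patient's change, including those who discontinue. This supports keeping EEC in the report. It does not supply the missing rate: a waterfall plot is a display, and prespecifying a subset does not remove the selection in it.

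Four stronger readings are tempting, and the documents do not support them.

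- *The plan rules out a pooled analysis.* It does not. The two subgroups are given as examples, so a pooled rate is permitted but undefined.
- *The 20% reference is an all-treated rate.* Its wording has no adherence condition, but it is extrapolated from a cited study's response at any time, and that study's denominator is not in the documents.
- *Section 8.3.5 already requires early drop-outs to count as PSA50 non-responders.* It covers tumour assessments missing because of rapid progression or toxicity. It does not cover PSA, withdrawal or non-adherence.
- *A full denominator always lowers the false-claim chance.* At 29 or 30 eligible treated patients it does not, under either response assumption in step 4.

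**Conclusion.** The point holds as a gap in the definition of the lead estimate. The rate to be compared with 20% comes from a subset selected after baseline, while the objective and target rate concern eligible or treated men, and no rate with that denominator is specified.

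The direction of bias depends on excluded patients responding less often than EEC patients, which is plausible but not documented. On that assumption the overstatement is at most about 3.5 points at the plan's 15%. It is smaller if some of the 15% are ineligible at baseline, since that allowance is an upper figure covering every reason for not becoming EEC. The effect on the final conclusion is narrow, as step 5 shows. The case for change is therefore an estimate that matches the question, not a guaranteed reduction in false claims. It should be fixed, but it does not undermine the trial.

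**What to change.** In 11.3.4 and 11.4.1:

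- Define the PSA50 rate in all eligible patients, with eligibility judged on baseline data, who receive at least one dose.
- Count anyone without a qualifying 8-week decline as a non-responder, including early discontinuations and missing PSA. State this as a new rule for PSA50, similar in direction to 8.3.5 but wider.
- Rest the comparison with 20% on this set. Keep EEC as a labelled efficacy (sensitivity) analysis reported beside it.
- Restate the precision (half-width at a 30% estimate: 0.099 at N = 27, 0.092 at N = 32) and the responder count needed: at least 9 at N = 27 to 30, at least 10 at N = 31 to 32.

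The change needs wording only and no extra patients, but it has a statistical cost. The point estimate may be lower. With a 30% EEC rate, 27 EEC patients have a 42.3% chance of a lower limit above 0.20. If exclusions never respond, that chance is unchanged at N = 28 to 30 but falls to 27.2% at N = 31 to 32. If they respond at half the EEC rate (15%), it is 36.4% at N = 31 and 38.8% at N = 32.
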